3.2.16 Absolute neutrophil count < 1500 mm 3 at screening

3.2.17 Hemoglobin concentration < 9 g/dL at screening

3.2.18 Patients without available lymphatics will be deemed unable to receive LYMPHA procedure.

3.2.19 Any reason (in addition to those listed above) that, in the opinion of the investigator, precludes full participation in the study

3.3 Informed Consent Process

All participants must be provided a consent form describing the study with sufficient information for participants to make an informed decision regarding their participation. Participants must sign the IRB approved informed consent prior to participation in any study specific procedure. The participant must receive a copy of the signed and dated consent document. The original signed copy of the consent document must be retained in the medical record or research file.

3.4 Randomization Procedures

Since this study was started with two groups (A and C), and randomized 13 patients to the control group A and 14 patients to the treatment group C. However, 7 of the 14 patients that were randomized to treatment group C did not receive LYMPHA surgery , were considered screen fails. 27 patients will be used in intent-to-treat (ITT) analysis, however, 7 screen fails will not be counted in the per protocol (PP) analysis. In the new 3-arm phase, the randomization procedures will happen during ALND surgery time. and 90 subjects will be allocated in a 1:1:1 randomization ratio into three groups. The clinic staff obtaining measurements will be blinded to the treatment group

A Randomized Clinical Trial of the LYMPHA procedure for the Prevention of Lymphedema after Axillary Lymphadenectomy

3.5 Study Timeline

Primary Completion:

The study will reach primary completion 24 months from the time the study opens to accrual.

Study Completion:

The study will reach study completion 36 months from the time the study opens to accrual (i.e., 2 year accrual and an additional 12 months to monitor recovery). Length of follow-up for each patient will be 12 months.

4. TREATMENT PLAN

All consenting patients presenting to breast oncologist's or [name] clinics who are candidates for breast cancer related axillary lymphadenectomy and satisfy the above inclusion and exclusion criteria will be given the option of study enrollment. Patients will be consented to treatment by either [name] or another physician that has met the appropriate prerequisite criteria for performing LYMPHA.

After informed consent is obtained, all subjects will undergo an initial study evaluation to establish the pre-operative baseline and to determine eligibility for randomization. Group A will undergo axillary lymphadenectomy alone, Group B will undergo axillary lymphadenectomy with soft tissue reinforcement using collagen scaffold, and Group C will undergo axillary lymphadenectomy with immediate lymphatic reconstruction (LYMPHA) using reverse mapping with the SPY System. Each of the baseline measures will be repeated over the 12 months of enrollment in the study according to the STUDY CALENDAR.

1. Indocyanine green lymphography: One of the most important advances in lymphedema staging and in lymphatic vessels detection is indocyanine green (ICG) lymphography [23-27]. In the early lymphedema stages this exam allows to detect percutaneously the lymphatic vessels of the whole limb, up to about 1 cm in depth from the skin surface, by an infrared camera visualization system after intra-dermal injection of ICG in the hand [24, 27]. The change in the lymphatic pattern and reduction in the ICG velocity [26] will be assessed. The healthy upper limb lymphatic pattern will be used as a baseline for each patient. A delay of more than 50% in ICG migration from the injection points to the axilla of the affected upper limb in comparison with the contralateral healthy upper limb will be used as an indication of lymphedema.

2. Limb volume. The volume of the at-risk and the contralateral arm of each subject will be measured through serial quantitation of the limb circumference at 4 cm intervals along its long axis. The procedure is performed with gauged tape to ensure a uniform stretching force. Using these measurements, the volume of the limb is calculated with the truncated cone approximation [20]. Pre- and post-treatment measurements for each subject will be performed by the same operator who, in all cases, will be blinded to the patients' treatment status and to pre-treatment measurement values at the time of the post-treatment assessment. The measured limb volumes at each evaluation will be utilized to generate two data points: the volume V_r of at-risk arm and the volume V_c of contralateral arm. These data will be used to determine a relative excess volume $E = ((V_r - V_c)/V_c) \cdot 100\%$ for each patient at the time of measurement [32]. Change in the relative

A Randomized Clinical Trial of the LYMPHA procedure for the Prevention of Lymphedema after Axillary Lymphadenectomy

excess volume will be determined at month 12 as $(E_{12}/E_0 - 1) \cdot 100\%$, where E_0 is the relative excess volume at baseline ($t=0$) and E_{12} is the relative excess volume at 12 months ($t=12$).

3. Skin thickness measurements: These will be performed with a Lange skinfold caliper (Beta Technology, Santa Cruz, CA). For each subject, at each assessment, three measurements will be obtained of both upper extremities: the dorsum of the hand; the midpoint of the volar aspect of the forearm; and the midpoint of the medial aspect of the upper arm. At the initial evaluation, a dermatographic pencil is used to mark the site of each measurement. Once the locations are determined, the exact distance of each location is measured from the wrist. These locations are re-utilized for serial measurements during the trial. The calipers will be calibrated prior to each use. The serial evaluations will be performed by the same operator for each subject, and the operator will be blinded to treatment status and to prior measurement values at the time of each assessment. Each reported skin thickness value represents the arithmetic sum of the three measurements/limb at that assessment. The change in the ratio of ipsilateral:contralateral skin thickness will be analyzed as a secondary endpoint.

4. Bioimpedance spectroscopy (BIS) will be performed with the Impedimed SFB7. A four-electrode configuration is used to non-invasively assess the extracellular and intracellular fluid contents of the limb [21]. Data were analyzed according to Cole theory [22], using the manufacturer's software (Impedimed Ltd.), to provide values for R_0 , the resistance of the extracellular fluid, including lymph, R_{t0} the resistance of total tissue fluid, and R_i , the resistance of the intracellular fluid. For the purposes of these investigations, the ratio of R_0 in the ipsilateral:contralateral limbs will be analyzed in each patient as a secondary endpoint.

5. Quality-of-life will be serially assessed, at baseline and at 12-months, using a validated instrument, the LYMQOL [28]. The LYMQOL is divided into four domains: Function, Appearance, Symptoms, and Mood, as well as yielding an overall quality-of-life score. These continuous variables will be analyzed as a secondary endpoint for intergroup comparisons.

A video recording of 1-2 cases in the study group may occur. The purpose of these videos would be to demonstrate the operative method. These recordings may also supplement eventual publications and scientific presentations. Only patients consenting to video recording will be affected. All videos will be deidentified (no facial identification possible). Videos will be kept in a secure, encrypted location and destroyed within 5 years following completion of the study. Photography will be routinely used pre- and postoperatively, with appropriate patient consent, in order to document aesthetic outcomes. Tissue samples will not be retained for future research.

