3.2 Exclusion Criteria

- 3.2.1 Primary lymphedema of the affected upper limb
- 3.2.2 Secondary lymphedema of the affected limb prior to the lymphadenectomy
- 3.2.3 Radiotherapy at the axilla before the study / surgery
- 3.2.4 Allergic reaction to porcine collagen or ICG
- 3.2.5 Receiving radiation therapy to the involved nodal basin in a period less than 4 weeks after the surgery
- 3.2.6 Concurrent participation in a clinical trial of any other investigational drug or therapy, regardless of indication, within 1 month before screening
- 3.2.7 Other medical condition that could lead to limb edema, such as (but not limited to primary lymphedema or acute venous thrombosis

A Randomized Clinical Trial of the LYMPHA procedure for the Prevention of Lymphedema after Axillary Lymphadenectomy

3.2.8 Other medical condition that could result in symptoms overlapping those of lymphedema in the affected limb (e.g., pain, swelling, decreased range of motion)

3.2.9 Either of the following, at the time of baseline evaluation: ipsilateral:contralateral limb volume ratio >1.1 or R0 bioimpedance ratio > 1.106 when the nondominant limb is at risk, and 1.134 when the dominant limb is at risk.

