4.2 Criteria for Removal from Study

Patients would be removed from the treatment plan in the event of patient withdrawal of consent, allergy, or other unforeseen deleterious events. The patients randomized to the intervention but did not receive the intervention due to unforeseeable reasons will be removed from the study and then replaced.

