10. MEASUREMENTS

10.1 Primary outcome measure: Incidence of lymphedema

The primary endpoint in this study is a binary outcome variable defined as the presence of lymphedema at Month 12 (“Yes”/”No”), based on the fulfilment of at least one of the following three criteria: (1) More than 10% increase in the relative excess volume of the affected limb; (2) More than 50% time delay of ICG migration from the injection points to the axilla of the affected upper limb in comparison with the contralateral healthy upper limb; or (3) Aggravation of one or more stages in Yamamoto’s classification of the dermal back flow and morphology of the lymphatic collectors.

The efficacy of the LYMPHA procedure will be determined by comparison between the LYMPHA group (Group C) and lymphadenectomy group (Group A).

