10.2.2 The ratio of ipsilateral:contralateral skin thickness measured by large skinfold calipers

10.2.3 The ratio of R0 in the ipsilateral:contralateral limbs measured using BIS

10.2.4 The excess volume pairwise comparison between the LYMPHA group and each of the two control groups. We will also compare the excess volume between the two control groups.

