12.2 Preliminary assessment

Since the study has stopped 2-arm recruitment and will start the new 3-arm recruitment, the current collected 2-arm data will be used to conduct a preliminary assessment, to check the comparability, safety and efficacy of the trial.

Preliminary assessment will evaluate the primary endpoint (presence of lymphedema) and secondary endpoints (skin thickness, BIS, and LYMPQOL). Both intent-to-treat (ITT) analysis and per protocol (PP) analysis will be explored.

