12.6.2 Sample size justification

The risk of lymphedema development is considered to be 30% in the surgical control group (group A), and studies have shown it is to be reduced to 4% when LYMPHA is applied during an axillary lymphadenectomy [12, 30]. With N=40 subjects (20 subjects per arm A and C) in the first stage, the power to stop after the first stage is 56%. Finally, with additional N=40 subjects (20 subjects per arm A and C) in the second stage, the overall power to stop at either the first or the second stage is 88%.

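### The only formula for change in relative excess volume divides by a signed, near-zero baseline, so the primary endpoint's volume criterion fires on trivial rises or cannot detect swelling at all

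*Protocol*

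**What the plan says.** Section 4, item 2 defines "a relative excess volume $E = ((V_r - V_c)/V_c") times 100%, where Vr is the volume of the at-risk arm and Vc that of the contralateral arm. It then fixes how change is computed: the change in relative "excess volume will be determined at month 12 as $(E_{12}/E_0 - 1"), times 100%, where E0 is the baseline value and E12 the month-12 value.

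Section 10.1 and the synopsis list three criteria for lymphedema at month 12, any one of which makes the primary endpoint positive. The first is "1) More than 10% increase in the relative excess volume of the affected limb". The other two rest on ICG lymphography (migration delay and Yamamoto stage). Section 10.1 does not refer back to the section 4 formula.

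Section 3.2.9 excludes patients whose baseline "ipsilateral:contralateral limb volume ratio >1.1". It sets no lower limit on that ratio. Sections 3.2.1 and 3.2.2 exclude existing lymphedema of the affected limb.

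**The concern.** A ratio to baseline works only if the baseline is positive and well away from zero. Here E0 is the difference between two arms before any lymphedema exists, so it should lie near zero and may have either sign. Dividing by it makes the 10% threshold depend on chance baseline asymmetry, and reverses the direction of the test when E0 is negative.

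Any one criterion suffices, so a false volume flag cannot be undone by normal ICG findings. False flags in both arms raise both event rates and shrink the difference between LYMPHA and lymphadenectomy alone. In the other direction, swelling in a patient with negative E0 is invisible to this component, though an ICG criterion may still detect it.

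**Working it through.** **Inputs from the protocol.** E = 100 x (Vr - Vc)/Vc and change = 100 x (E12/E0 - 1) (section 4, item 2). Threshold: more than 10% (section 10.1). Baseline volume ratio at most 1.1 (section 3.2.9), so E0 <= 100 x (1.1 - 1) = 10%. Planned event rates 30% and 4% (section 12.6.2). Alpha 5% (section 12.1).

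**Step 1: solve 100 x (E12/E0 - 1) > 10 for E12.**
- E0 > 0: E12 > 1.1 x E0, a rise of more than 0.1 x E0. With E0 <= 10 the threshold is at most 1.0 point. It is 0.5 points at E0 = 5 and 0.1 at E0 = 1. On an assumed 2000 mL arm, 1.0 point is 20 mL and 0.1 point is 2 mL.
- E0 = 0: undefined.
- E0 < 0: multiplying by a negative number turns the inequality round, giving E12 < 1.1 x E0. The arm must become relatively smaller.

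| E0 | E12 | Actual change (points) | Formula | Criterion met? |
|---|---|---|---|---|
| 1.0 | 1.2 | +0.2 | +20% | yes |
| 10 | 11.1 | +1.1 | +11% | yes |
| -2 | +10 | +12 | -600% | no |
| -2 | -2.5 | -0.5 | +25% | yes, if applied mechanically |

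As a numerical check, 1,000,000 random pairs with E0 < 0 and E12 > E0 were scored. None met the criterion.

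**Step 2: how often this would happen.** The protocol gives no standard deviations, so these are assumptions: true asymmetry with mean 0, 1 or 2 and SD 3, 4 or 5 points; measurement SD 0.5, 1 or 2 points at each visit; measured E0 at most 10. That makes 27 scenarios, with 2,000,000 simulated patients in each.

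| | Printed formula | E12 - E0 > 10 points |
|---|---|---|
| No true change: flagged | 29.4-37.6% | 0-0.02% |
| Same, if a fall in E never counts | 14.7-27.5% | 0-0.02% |
| True +12 points: missed by this component | 25.7-51.6% | 0.2-23.8% |
| True +15 points: missed by this component | 25.7-51.7% | 0-3.8% |

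Under the printed formula more than 99.9% of the misses at +12 points have E0 < 0, which is why a larger swelling does not reduce them. Under the difference rule the misses come from measurement error near the cut-off. At measurement SD 2, the SD of the difference is 2 x sqrt(2) = 2.83, and a true +12 lies only 2/2.83 = 0.71 SD above the threshold, giving about 24% missed.

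**Step 3: the plan's own power.** Section 12.6.2 gives 56% at the first stage and states that "the overall power to stop at either the first or the second stage is 88"%. A two-look z test with unpooled variance, a Pocock bound of 2.178, and 20 then 40 per arm gives 56.2% and 88.2%, so those figures reproduce.

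**Step 4: illustration of dilution.** If a share f of true negatives is falsely flagged in each arm, and every true case is still detected, the observed rate is p + f x (1 - p).
- f = 15%: 30 + 0.15 x 70 = 40.5% against 4 + 0.15 x 96 = 18.4%.
- f = 30%: 30 + 0.30 x 70 = 51.0% against 4 + 0.30 x 96 = 32.8%.

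Exact two-sided Fisher power at alpha 0.05, single look:

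| False flags | 30 per arm (section 2.4) | 40 per arm (section 12.6.2) |
|---|---|---|
| none | 68.9% | 86.9% |
| 15% | 36.9% | 49.8% |
| 20% | 30.1% | 41.4% |
| 30% | 21.4% | 30.7% |

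**The case against.** The strongest reply is that section 10.1 never cites the section 4 formula, so its 10% may mean percentage points, with the ratio serving only as a descriptive measure. That may well be the intent. But section 4 gives the only definition of change for the same quantity at the same visit, and nothing in the protocol states a percentage-point rule. The two readings classify the same patients in opposite ways, so the text needs correcting whichever was meant.

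It is also fair to say that the fault touches one criterion of three and that the ICG criteria may recover missed swelling. That stands, and it is why the miss rates above belong to the component and not to the endpoint. It does not help with false flags.

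The power figures are open to several objections, and these stand as limits. The spreads are assumed. The 15-30% range is a rounded choice that runs from the low end of the narrower reading to about the low end of the mechanical one. Full sensitivity is assumed although the component misses cases. The 30% and 4% come from outside literature, and the protocol does not say which lymphedema definition produced them. Two-sided alpha is assumed. The 40-per-arm figure is a single-look Fisher calculation, not the two-stage design of section 12.6.2. The 69% starting point at 30 per arm is below the planned power for reasons unrelated to this formula.

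Finally, a difference of more than 10 points is not the only workable rule; a month-12 volume ratio above 1.1 is another. That would measure a level, however, whereas section 10.1 asks for an increase.

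**Conclusion.** The point holds and must be fixed. From the protocol's own definitions, the volume criterion has a threshold of at most 1 percentage point when E0 is positive, is undefined at zero, and cannot be met by swelling when E0 is negative. No assumption is needed for this, and no reading was found under which the printed formula works for this baseline.

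The size of the effect is conditional. Under the assumed spreads, roughly 15-38% of unchanged patients would be flagged, depending on whether a fall in E can count, and about a quarter to a half of clear swellings would be missed by this component. The fall in power, from 69% to 37-21% at 30 per arm, shows how much false flags could cost; it is not a forecast for this trial. Confidence is high in the algebra and lower in the net effect on the composite endpoint.

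**What to change.** In section 4, item 2, define change as E12 - E0 in percentage points. In section 10.1 and the synopsis, state criterion (1) as E12 - E0 greater than 10 percentage points, with a reference to section 4. Section 10.2.4 ("The excess volume pairwise comparison between the LYMPHA group and each of the two control groups") names excess volume and not its ratio change, so it needs the same definition only if it is analysed as change from baseline.

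The cost is one formula and two sentences in an amendment. Both arm volumes are already planned at baseline and month 12, so no new measurement is needed.

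The drawback is a mid-trial change to a component of the primary endpoint. Section 12.2 says "Preliminary assessment will evaluate the primary endpoint (presence of lymphedema) and secondary endpoints", so the change should be settled before that look and without reference to arm-level results, and the amendment should record this. Only two-arm patients with both volumes can be rescored. The 7 of 27 who did not receive LYMPHA may lack month-12 volumes, because section 4.2 says such patients "will be removed from the study and then replaced". Sections 3.4 and 12.1.1 nevertheless keep all 27 in the intent-to-treat analysis, and the protocol does not say whether those volumes exist.

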4.1 General Concomitant Medication and Supportive Care Guidelines

There are no known interactions of medications with the intraoperative use of indocyanine green, which we routinely use to assess nipple perfusion during mastectomy. Patients with an allergy to iodine will be excluded. Concomitant radiotherapy is an exclusion criterion for study participation.

Procedures performed are a normal part of clinical management for this condition. Patients in all three groups are subject to the baseline risks of surgical intervention, including but not limited to

A Randomized Clinical Trial of the LYMPHA procedure for the Prevention of Lymphedema after Axillary Lymphadenectomy

bleeding, infection, scar, injury to surrounding structures, risks of anesthesia, and need for further surgery.

4.2 Criteria for Removal from Study

Patients would be removed from the treatment plan in the event of patient withdrawal of consent, allergy, or other unforeseen deleterious events. The patients randomized to the intervention but did not receive the intervention due to unforeseeable reasons will be removed from the study and then replaced.

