2.4 Study Design

We propose a randomized clinical trial to determine the efficacy of the LYMPHA procedure in breast cancer patients undergoing axillary lymphadenectomy.

Up to 100 subjects will be enrolled in the trial; they will undergo either lymphadenectomy, lymphadenectomy with soft tissue reinforcement (STR) or lymphadenectomy with LYMPHA. Subjects must meet all additional defined inclusion and exclusion criteria.

Please note that soft tissue reinforcement is common practice and used as the standard of care in some lymphedema centers. The addition of this group is important because it allows a comparison of LYMPHA to a currently commonly practiced alternative and the ability to assess for superiority of the LYMPHA procedure. In short, at Stanford, we perform soft tissue reinforcement with collagen scaffolding commonly and would like to start including these patients in our prospective analysis/study.

All patients that are enrolled will be randomized into one of three groups: Group A (surgical control group 1) – the patients will undergo lymphadenectomy alone with simple wound closure, Group B (surgical control group 2) – the patients will undergo lymphadenectomy with soft tissue reinforcement using a collagen scaffold, or Group C (treatment group) - the patients will undergo lymphadenectomy and LYMPHA at the time of wound closure as an adjunct to lymphadenectomy procedure.

Randomization will occur after it has been determined that patients are eligible for the trial intraoperatively. Patients are deemed eligible for the trial intraoperatively if ALND is performed and there are available lymphatics to bypass.

The study will be double blind and randomized. Each patient will be randomized to either the treatment or control group 1 or 2 and will be blinded to their group. While the surgeons will not be blinded, all personnel who track outcomes in clinic will be blinded. The primary outcomes that the protocol is designed to evaluate include efficacy, safety, and impact on the quality of life.

The study was started with 2-arm design (Group A and Group C). A preliminary assessment to the trial effects will be conducted using the current collected data. After the revised protocol is approved, the study will recruit subjects in the new 3-arm phase: 90 subjects (30 subjects per arm in the three groups (Groups A, B, C)

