5. INVESTIGATIONAL AGENT/DEVICE/PROCEDURE INFORMATION

5.1 Investigational Agent/Device/Procedure

As described in section 2.2, the intervention arm involves the use of the LYMPHA procedure at the time of axillary lymphadenectomy, specifically, anastomosing lymphatics to nearby veins distal to the site of injury to facilitate normal lymphatic drainage [11]. This procedure is a normal part of clinical management for this condition. The purpose of this study is to more accurately elucidate the efficacy and role of this procedure. Nanofibrillar collagen scaffolds are FDA approved product for soft tissue reinforcement and is routinely used for this indication at the surgical site to enhance tissue repair.

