12.1.1 Randomization

Since this study was started with two groups (A and C), and randomized 13 patients to the control group A and 14 patients to the treatment group C. However, 7 of the 14 patients that were randomized to treatment group C did not receive LYMPHA surgery, were considered screen fails, Therefore in the preliminary assessment, 27 patients will be used in intent-to-treat (ITT) analysis, however, 7 screen fails will not be counted in the per protocol (PP) analysis. In the new 3-arm phase, the randomization procedures will happen during ALND surgery time. and 90 subjects will be allocated in a 1:1:1 randomization into three groups. The clinic staff obtaining measurements will be blinded to the treatment group.

A Randomized Clinical Trial of the LYMPHA procedure for the Prevention of Lymphedema after Axillary Lymphadenectomy

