12.4.1 Analysis Population

All participants will be included in ITT (intent to treat) analysis. Participants who had screen fail will not be included in PP (per protocol) analysis. Missing data and non-adherence to protocol will be reported and its impact will be analyzed.

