12.5.2 Analysis Plan

All secondary outcome measures (the ratio of at-risk: contralateral skin thickness; ratio of R0 in the at-risk: contralateral limbs; and total LYMQOL score) are continuous scores and will rely on generalized linear mixed models (GLMMs). GLMMs properly account for correlations induced by repeated measurements within subjects and automatically handle missing data, as noted above. To make the most efficient use of our data we will fit a single model using all time points for each outcome. To allow for the possibility that the outcome may not have a linear relationship with time, we will treat time as a categorical variable. Treatment group and time main effects, along with two-way interactions of time and group, will be used as independent variables and the time by group interaction term will be used to determine the statistical significance of the difference in the outcome between the LYMPHA group and control groups.

A Randomized Clinical Trial of the LYMPHA procedure for the Prevention of Lymphedema after Axillary Lymphadenectomy

The primary analysis will use all subjects enrolled and assigned to treatment, categorized by their planned treatment (intention to treat, ITT). A sensitivity analysis will use the set of subjects enrolled and treatment-assigned in the study who completed the study protocol, categorized according to treatment actually received (per protocol, PP).

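### Protocol section 4.2 removes and replaces patients randomised to the intervention who do not receive it, which contradicts the protocol's own ITT rule

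*Protocol*

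**What the plan says.** Protocol section 4.2 (Criteria for Removal from Study) states that patients "randomized to the intervention but did not receive the intervention due to unforeseeable reasons will be removed from the study and then replaced".

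The analysis sections say something else. Section 12.4.1, under the primary analysis, states: "All participants will be included in ITT (intent to treat) analysis". Section 12.5.2 adds: "The primary analysis will use all subjects enrolled and assigned to treatment, categorized by their planned treatment", and makes the per-protocol (PP) set a sensitivity analysis.

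The protocol has already met this situation. Section 12.1.1 reports that "7 of the 14 patients that were randomized to treatment group C did not receive LYMPHA surgery, were considered screen fails". Section 3.4 then says that "27 patients will be used in intent-to-treat (ITT) analysis, however, 7 screen fails will not be counted in the per protocol (PP) analysis".

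Section 5.1 indicates which arm is meant: "the intervention arm involves the use of the LYMPHA procedure at the time of axillary lymphadenectomy". For the 3-arm phase, section 2.4 says: "Randomization will occur after it has been determined that patients are eligible for the trial intraoperatively".

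**The concern.** A patient who has been randomised cannot be taken out of the study, have the place filled by someone else, and also be analysed in the assigned arm. The two-arm phase kept such patients in ITT; section 4.2 prescribes the opposite for the same event.

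The rule most likely acts on Group C alone. Section 5.1 ties the intervention to LYMPHA, and no matching rule exists for Groups A or B, although section 4.2 does not say so outright. Group C would then be selected after randomisation while Group A keeps everyone assigned. Comparing C with A is the main test in sections 10.1 and 12.1.

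Section 4.2 also does not say whether follow-up continues after removal. The primary endpoint is read at Month 12. The visit summary in section 12.2 places postoperative limb measurements and ICG lymphography only at the optional 9-month visit and at 12 months. A patient who leaves around surgery would have no postoperative lymphedema assessment, so no later analysis plan could restore the ITT result.

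**Working it through.** **Inputs.** Risk 30% in Group A and 4% in Group C (section 12.6.2); 5% significance level (section 12.1), taken as two-sided because sidedness is not stated; Fisher's exact test (section 12.4.2); 30 per arm in the 3-arm phase (section 2.4) and 40 per arm in the power statement (section 12.6.2).

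**The plan's own figure.** Section 12.6.2 gives 56% power at the first stage (20 per arm) and 88% overall (40 per arm). A two-look z test with unpooled variance and a Pocock boundary (critical value 2.178 at both looks) gives 56.2% and 88.2%, so the planning inputs are understood. A single exact Fisher test at 40 per arm gives 86.9%.

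**Effect of the rule on the analysis set.** Applied to the two-arm phase, removal would have cut the ITT set from 27 (13 in A, 14 in C) to 20 (13 in A, 7 in C): half of Group C and none of Group A.

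**Effect on the estimate if LYMPHA works.** Let f be the share of Group C not receiving LYMPHA. The protocol gives no f for the 3-arm phase; 10% to 20% is assumed. Non-receivers are assumed to carry the 30% control risk.

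ITT risk in C = (1 − f) × 0.04 + f × 0.30

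- f = 0.10: 0.036 + 0.030 = 0.066; difference 0.300 − 0.066 = 23.4 points
- f = 0.20: 0.032 + 0.060 = 0.092; difference 20.8 points
- with removal, C stays at 0.04; difference 26.0 points

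The two-arm share of 7/14 would give 0.170 and 13.0 points. That is an upper illustration only: those patients stay in ITT, and the 3-arm phase randomises after available lymphatics are confirmed.

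**Effect if LYMPHA does nothing.** Let r be the risk in those removed, with 30% overall.

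Risk left in C = (0.30 − f × r) / (1 − f)

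At f = 0.10:

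| r | Risk left in C | Bias |
|---|---|---|
| 15% | 31.7% | 1.7 points against LYMPHA |
| 20% | 31.1% | 1.1 points against |
| 30% | 30.0% | none |
| 40% | 28.9% | 1.1 points in favour |
| 50% | 27.8% | 2.2 points in favour |

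**Power when everyone is kept.** Exact two-sided Fisher test, Group A at 30%:

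| Non-receipt | Risk in C | 30 per arm | 40 per arm |
|---|---|---|---|
| 0% | 4.0% | 68.9% | 86.9% |
| 10% | 6.6% | 54.1% | 73.4% |
| 20% | 9.2% | 40.8% | 58.1% |

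The smallest size that restores 86.9% is 56 per arm at 10% non-receipt and 75 per arm at 20%.

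**The case against.** The best defence is that both rules can be met: replacement restores the number treated, sections 12.4.1 and 12.5.2 fix the analysis set, and the seven two-arm patients were handled in just that way. That would work if follow-up continued. But the text says removal is from the study, under a heading about removal from the study, and nothing in it supports continued follow-up. The defence shows what the sponsor may intend, not what section 4.2 instructs.

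Second, the study calendar in section 9 uses an intervention column that covers all three procedures, so the rule may reach Group B, or on its face every arm. This stands as an uncertainty. Group A has simple closure and would seldom lose anyone, so the imbalance between C and A would remain.

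Third, the size is assumed. Randomisation now follows confirmation that lymphatics are available, so non-receipt may be well below 10%; at 10% it is about 3 of 30 patients. The gap between 26.0 and 23.4 points is a difference between two estimands under a real effect, not a false benefit. The null-case bias is small beside a standard error of √(2 × 0.30 × 0.70 / 30) = 0.118, about 12 points. All of this is fair. It limits the expected size but does not remove the contradiction.

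Finally, the labelling of randomised patients as screen failures and the two descriptions of the PP set are editorial. That is accepted: "Participants who had screen fail will not be included in PP (per protocol) analysis" in section 12.4.1 can be read together with the completer definition in section 12.5.2.

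**Conclusion.** The concern holds. Section 4.2 is wrong as written: it conflicts with section 12.4.1, with section 12.5.2, and with the handling of the two-arm patients in sections 3.4 and 12.1.1. It should be corrected before any 3-arm patient is removed, because lost Month 12 follow-up cannot be recovered.

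The contradiction and the selection of Group C follow from the text, given that the intervention means LYMPHA. The size does not. An overstatement of 2.6 to 5.2 points against ITT (26.0 − 23.4 and 26.0 − 20.8) depends on the assumed 10% to 20% non-receipt and on control risk in non-receivers. With no treatment effect, the direction of bias depends on the prognosis of those removed, which the protocol does not give.

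**What to change.** Replace the second sentence of section 4.2 with wording such as: *Patients randomised who do not receive the assigned procedure stay in follow-up to Month 12 unless consent is withdrawn, and are analysed in the assigned arm. Any further enrolment is in addition to, not in place of, these patients. This applies to Groups A, B and C.* The first sentence, on reasons for leaving the treatment plan, can stay. Section 4.3 links forgoing LYMPHA to withdrawing from the study and should be read alongside the new wording so that the two agree.

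As tidying, describe these patients in sections 3.4, 12.1.1, 12.4.1 and 12.5.1 as not having received the assigned procedure, exclude them only from the supportive PP analysis, and use one PP definition in sections 12.4.1, 12.5.1 and 12.5.2.

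The direct cost is an amendment and Month 12 visits for the non-receivers. The real cost is the power loss shown above. Restoring about 87% by size alone would need 56 or 75 per arm, which is 3 × 56 = 168 or 3 × 75 = 225 patients across three arms. The stated total is 100, which the 27 + 90 = 117 patients already described exceed. The sponsor should either acknowledge the loss or cover it with a stated amount of added enrolment.
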